6.7 Outcome Research Assessment

Note: As of Protocol Version 7/ Amendment 6, quality of life assessments are no longer being performed.

Throughout the clinical trial period, patients will be asked about their quality of life via the Quality of Life questionnaires EQ-5D-5L.

The EQ-5D-5L is a standardized instrument developed by the EuroQol Group to describe and value health related quality of life. The instrument comprises the following five dimensions: mobility, self-care, usual activities, pain/discomfort and anxiety/depression. Each dimension is rated by the patients on a 5 point scale as having 'no problems' (a score of 1), 'slight problems (a score of 2), 'moderate problems', (a score of 3), 'severe problems', (a score of 4) and 'extreme problems', (a score of 5) based on descriptive examples: the scores are not intended to be summed. Present overall state of health is also to be rated on a vertical visual analogue scale (approximately 20cm in length) from 0 to 100 (the higher the number the better quality of life.

The EQ-5D-5L will be performed at screening (any time prior to first dose) and then monthly on Day 1 of Cycles 1 to 4 (completed prior to all other D1 procedures) for all Phase 2 patients.

Patients should self-complete the EQ-5D-5L and return to the site. Data will then be entered into the patient's eCRF.

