9.2.8 Quality of Life Analysis

Quality of life, as assessed by the EQ-5D-5L, will be analyzed for patients in the EE and FAS. EQ-5D-5L data will be summarized from the screening visit through cycle 4 for the FAS and EE Analysis sets (Phase 2). The number and percentage of patients reporting each score per dimension will be summarized, as well as the number reporting some problems on that dimension (score > 1). Also the change from baseline in the number reporting some problems in each dimension will be reported (raw and percent change). Additional analyses and techniques for handling missing data will be described in the SAP.

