SAP	statistical analysis plan
SA	single agent
SCT	stem cell transplant
SD	stable disease
SMQ	Standardised MedDRA Query
SOC	system organ class
TEAE	treatment emergent adverse event
t _{1/2}	terminal elimination half life
T _{max}	time to maximum plasma concentration
VAS	visual analogue scale
Vd/F	volume of distribution
WHO	World Health Organization

I. Introduction

This is a phase 1/2, multicenter, open-label study of FT-2102 as a single agent (SA) and in combination with azacitidine or cytarabine in patients with acute myeloid leukemia (AML) or myelodysplastic syndrome (MDS) with an IDH1 mutation.

This Statistical Analysis Plan (SAP) is based on version 5 of Protocol 2102-HEM-101.

This SAP will govern the analysis of data from this study. The plan may be modified until the time of database lock. Any deviations from the analysis plan, including any after the time of database lock, will be documented as such in the study report.

Any protocol-specified statistical analyses for pharmacokinetics (PK), or PK/PD in relationship with clinical safety and clinical activity will be prepared by related function in a separate document.

II. Protocol Objectives

A. Primary

The primary objectives are:

Phase 1

• To determine the maximum tolerated doses (MTDs), the maximum evaluated doses (MEDs), dose-limiting toxicities (DLTs), and the Recommended Phase 2 doses (RP2Ds) of FT-2102 as a single agent in combination with azacitidine, and in combination with cytarabine in patients with AML or MDS harboring an IDH1-R132 mutation.

Phase 2

• To evaluate the antileukemic and antimyelodysplastic activity of FT-2102 as a single agent or in combination with azacitidine in patients with AML or MDS, respectively harboring an IDH1-R132 mutation

B. Secondary

The secondary objectives are:

Phase 1

- To determine the pharmacokinetics (PK) of FT-2102 as a single agent and in combination with azacitidine or cytarabine
- To observe patients for any evidence of antileukemic or antimyelodysplastic activity of FT-2102 as a single agent and in combination with azacitidine or cytarabine

Phase 2

- To confirm the safety of FT-2102 as a single agent and in combination with azacitidine in select patient populations
- To evaluate additional measures of the antileukemic or antimyelodysplastic activity of FT-2102 as a single agent and in combination with azacitidine
- To determine the PK of FT-2102 as a single agent and in combination with azacitidine

C. Exploratory

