The imputation will be done according to methodology proposed by Diehr et al. (2007). Data will be imputed for missing assessments of Phase 2 patients and will be performed separately for each of five dimensions and VAS score of the EQ-5D-5L. VAS and each of the dimensions is represented by QOL in the imputation algorithm below. The five domains of EQ-5D-5L responses are ordered categories ranging from "no problems" to "extreme problems." Answers will be converted to a 5-point scale in which 1=no problems and 5= extreme problems. The VAS score of EQ-5D-5L ranges from 0 (worst health) to 100 (best health).

• Compute QOL-transformed (QOLt):

QOL score will be transformed to the probability that a person will have good QOL next cycle (have domain QOL \leq 3 next cycle; or have VAS QOL \geq 80), estimated from his QOL this cycle. All transition pairs (two values of QOL for the same person 1 cycle apart) will be used in the longitudinal data, and the transformation parameters will be estimated from a logistic regression of a binary variable "Good QOL 1 cycle later" on "QOL now." In the longitudinal data for each patient a column with one space for every cycle of that patient's potential follow-up will be created. The regression model will be as follows:

logit (Good QOL 1 cycle later) = a + b*QOL now.

The estimated probability of having good QOL 1 cycle later as a function of current QOL is then:

QOLt = Prob(Good QOL 1 cycle later | QOL) = exp(a+b*QOL)/(1+exp(a+b*QOL)).

• Compute QOL transformed with deaths added (QOLtd):

Set the values of QOLt for the cycles after a patient died to zero. For cycles after death, patients should receive a zero because they have no probability of having good QOL one cycle later.

• Compute QOLtd imputed (QOLtdi):

QOL for cycles when patients were alive but had no QOL data will be imputed from the regression of QOLtd on the logarithm of time from death (or time from the analysis date if still alive).

Calculation of time variable Cycle before death/end of follow-up (CBD):
 CBD = Cycle before death = cycle minus the integer part of (#days survived/28) + 1.

or

CBD = Cycle before end of follow-up = cycle minus the integer part of (#days on study/28) + 1

Unobserved cycles (e.g. due to missed visit, or time between last observed cycle and death when subject was alive but did not provide data) before deaths or end of followup will be imputed.

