Line plots showing the mean (+/- SE) bone marrow blasts, ANC count, hematocrit, platelet count will be presented over time on Day 1 for cycles 1-15 for patients in the Phase 2 Cohort 1 FAS and EE analysis set by best response (CR/CRh, non-CR/CRh responders, and non-responders).

Efficacy Profiles

For IA2, For those patients who have a best overall response of PR or better, patient plots of ANC, platelet count, hemoglobin, and bone marrow blasts (analyzed as described above) will be produced for all patients in the Phase 2 Cohort 1 FAS and for patients in the Phase 1 FAS whose starting dose of FT-2102 was 150 mg BID.

C. Quality of Life Analysis

The EQ-5D-5L consists of five dimensions: mobility, self-care, usual activities, pain/ discomfort, and anxiety/depression. Each dimension has 5 levels of health state: no problems, slight problems, moderate problems, severe problems and extreme problems. The patient indicates his/her health state by selecting the most appropriate statement in each of the five dimensions. This decision results in a 1-digit number that expresses the level selected for that dimension. The digits for the five dimensions can be combined into a 5-digit number that describes the patient's health state. Present overall state of health is also to be rated on a vertical visual analogue scale (VAS) from 0 (worst health) to 100 (best health). This assessment was only performed on Phase 2 patients. EQ-5D-5L data will be summarized from the screening visit through cycle 8 for the FAS (Phase 2) and EE analysis sets (Phase 2).

Five domains of EQ-5D-5L

The number and percentage of patients reporting each score per dimension will be summarized, as well as the number reporting some problems on that dimension (score >1). Also, the change from baseline in the number reporting some problems in each dimension will be reported (raw and percent change). An additional summary table will be produced that summarizes the EQ-5D-5L data by best response (3 groups: CR/ CRh, Other Responders, Non-Responders). Missing data will be imputed as described in Section VI.C.

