Appendix 1 Schedule of Event

Study Procedures	Pre-	Screening					Cycl	e 1	-	-				Сус	cle 2	-		Cycle 3 and Beyond	End of Treatmentª	28-day Follow- up ^b	Survival Follow- up
Days	(Optional)	D1)	D1	D2	D5 ± 1D	D8 ± 1D	D12 ± 2D	D15 ± 2D	D19 ± 2D	D22 ± 2D	D26 ± 2D	D1 ± 2D	D2 ± 2D	D4 ± 2D	D8 ± 2D	D15 ± 2D	D22 ± 2D	D1 ± 3D	± 7D	+ 7D	q 3 mo
Signed Informed Consent ^e		X ^c																			
Complete Medical History ^{d}		Х																			
Concomitant Medications		X	Х	Xe		Х		Х		Х		Х				Х		Х	Х	Х	
Height and Weight ^f		Х	Х									Х						Х	Х		
Vital Signs ^g		Х	Х			Х		Х		Х		Х						Х	Х		
ECOG PS		Х	Х									Х						Х	Х		
Physical Examination		Х	Х			X ^{h}		X ^h		X ^h		$X^{\underline{h}}$				X ^h		$X^{\underline{h}}$	Х		
Serum or Urine Pregnancy Test ⁱ		Х	х									Х						Х	Х		
12-lead Electrocardiogram ⁱ		Х	Xi			Xi		Xi		Xi		Х				Xi		Х	Х		
Holter Monitoring (Phase 2 only) ^k			Х	Х								Х	Х								
Clinical Serum Chemistries ^{1, m}		Х	Х		X ⁿ	Х	X ⁿ	Х	X ⁿ	Х	X ⁿ	Х			X ⁿ	Х	X ⁿ	Х	Х		
CBC with Differential and Platelet Count ^{m.o}		Х	х		X n	Х	X ⁿ	Х	X ⁿ	Х	X ⁿ	Х			X n	Х	X ⁿ	Х	Х		
Coagulation Parameters ^p		Х										Х									
Bone Marrow Aspirate ^q		Х										Х						Х	Х		
Urinalysis ^{m, r}		Х	Х									Х						Х	Х		
Adverse Event Monitoring										C	ontinuo	us								X	
Pharmacokinetics (Peripheral Blood) ^s			Х	Х		Х		Х		Х		X ^t	Х	Х		Х		Х			

Study Procedures	Pre-	Screening					Cycl	e 1						Сус	cle 2			Cycle 3 and Beyond	End of Treatment ^a	28-day Follow- up ^b	Survival Follow- up
Days	(Optional)	(D -14 to D1)	D1	D2	D5 ± 1D	D8 ± 1D	D12 ± 2D	D15 ± 2D	D19 ± 2D	D22 ± 2D	D26 ± 2D	D1 ± 2D	D2 ± 2D	D4 ± 2D	D8 ± 2D	D15 ± 2D	D22 ± 2D	D1 ± 3D	± 7D	+ 7D	q 3 mo
Pharmacodynamics (Peripheral Blood) ^{u}	X⊻	Х	X	х		Х		Х		x		Х	X	X		Х		Х			
EQ-5D-5L (Phase 2 only)		X ^w										Х						Х	Х		
Study Drug Diary ^x			Х									Х						Х			
Study Drug Administration ^{y,z,aa}				D	rug wil	ll be gi	iven in a	accorda	nce wit	h the do	sing scl	hedules	for FT	-2102,	azacit	idine an	d LDA	С			
Survival ^{bb}																					Х

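### EQ-5D-5L is summarised to Cycle 8 although the current protocol collects it only to Cycle 4, and the imputation rule does not separate missed from unscheduled assessments

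*SAP*

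**What the plan says.** The SAP Introduction names its parent document: "This Statistical Analysis Plan (SAP) is based on version 5 of Protocol 2102-HEM-101". SAP XI.C then says that "EQ-5D-5L data will be summarized from the screening visit through cycle 8", for the Phase 2 FAS and the EE set. It sends the reader to VI.C for missing values, in both the domain and the VAS parts.

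SAP VI.C sets a general scope: "Data will be imputed for missing assessments of Phase 2 patients". A mixed model fills each cycle up to death or end of follow-up in which the patient was alive and has no score. The two examples given are a missed visit and the stretch between the last observed cycle and death. SAP XI.C says that imputed values are flagged in the listing and says nothing of the kind for tables or charts. SAP Appendix 1 marks EQ-5D-5L at screening, C2D1, Day 1 of "Cycle 3 and Beyond" and End of Treatment.

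Protocol 9.2.8 has a shorter window: "EQ-5D-5L data will be summarized from the screening visit through cycle 4". Protocol 6.7 sets collection at screening and "then monthly on Day 1 of Cycles 1 to 4", and carries the note "As of Protocol Version 7/ Amendment 6, quality of life assessments are no longer being performed". The EQ-5D-5L row in protocol Appendix 1 ends at Cycle 4. Appendix 2, for patients enrolled after Version 7, has no such row, and 6.1.3 removes the questionnaire from their screening visit.

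**The concern.** The two documents give different windows for the same summary. By itself that would be a wording mismatch. It becomes a data question because the imputation rule is not limited to assessments that were due. A cycle at which nobody was asked to complete the questionnaire counts, on the text, as a cycle without data and is filled by the model.

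The by-visit domain tables, the percentage with a VAS score below 80, and the VAS change summaries would then combine patient answers with model output, unmarked. The mix would vary by cycle and by the protocol version a patient was under, so a pattern over the later cycles could partly reflect the imputation model. The rounding rule adds to this. VI.C rounds imputed values up, so any imputed domain value above 1 becomes at least 2 and counts as having some problems. That percentage can shift simply because the imputed share rises.

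**Working it through.** **1. The two windows.** SAP XI.C ends at Cycle 8; protocol 9.2.8 ends at Cycle 4. Both are current text. The SAP's electronic signing record is from February 2023 and the protocol is dated August 2020, so the SAP was not brought into line.

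**2. Scheduled time points.** Take the SAP window as screening plus Cycles 2 to 8: 1 + 7 = 8 time points. Cycle 1 Day 1 is not counted separately, because the schedule tables mark the pre-dose assessment under screening.

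| Schedule | Scheduled of 8 | Scheduled of Cycles 5–8 |
|---|---|---|
| SAP Appendix 1 (protocol version 5) | 8 | 4 of 4 |
| Current protocol 6.7 and Appendix 1 | 4 (screening, C2, C3, C4) | 0 of 4 |
| Enrolled after Version 7 (Appendix 2, 6.1.3) | 0 | 0 of 4 |

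**3. The imputation rule applied to each group.**
- *Treated on the version 5 schedule:* scores at Cycles 5–8 can be observed. Imputation covers missed visits and time alive after treatment ends, because SAP Appendix 1 does not place the questionnaire in survival follow-up.
- *Followed on the current schedule:* every score at Cycles 5–8 is imputed.
- *Enrolled after Version 7:* every score is imputed, and the prediction uses no questionnaire answer from that enrolment. Protocol 6.1 gives transfers from Cohort 1 to Cohort 3 or Cohort 6 as its example.

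**4. Illustration for the first group.** This asks how much would be imputed even where Cycles 5–8 were scheduled. The protocol synopsis expects about 26 weeks of treatment. Everything else here is assumed: exponential treatment duration with 26 weeks as mean or median, exponential survival with median OS of 6 to 18 months, and full completion while on treatment. At Day 1 of cycle c, w = 4(c − 1) weeks.

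- On treatment: on(w) = exp(−r·w), with r = 1/26 (26 as mean) or ln 2/26 (26 as median).
- Alive: al(w) = exp(−ln 2·w/M), with M = median OS in months × 30.4375/7.
- Imputed share among the living = 1 − min(on, al)/al.

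Worked case, 26 weeks as mean and median OS 18 months (M = 78.27 weeks):
- Cycle 5: w = 16, on = 0.540, al = 0.868, share = 1 − 0.540/0.868 ≈ 0.38.
- Cycle 8: w = 28, on = 0.341, al = 0.780, share = 1 − 0.341/0.780 ≈ 0.56.

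| Median OS | 26 wk as mean: C5 to C8 | 26 wk as median: C5 to C8 |
|---|---|---|
| 6 months | 17% to 28% | about 0% |
| 9 months | 28% to 44% | 13% to 22% |
| 12 months | 33% to 51% | 19% to 31% |
| 18 months | 38% to 56% | 25% to 39% |

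The share passes 50% only at Cycle 8 (12 months) and Cycles 7 and 8 (18 months), in both cases with 26 weeks as the mean.

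**5. Where the scores go.** SAP VI.I limits the EE set to Cohort 1 and drops EE analyses from the final CSR. Roll-over records in Cohorts 3 and 6 can therefore reach only the FAS summaries. The stacked bar charts cover Cohort 1 EE alone, so those records cannot enter them.

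**The case against.** A reader might infer that the Cycle 5–8 results would be mainly imputed, or that half the reported time points, and all those after Cycle 4, lack scheduled collection. The documents do not support this. Those fractions come from the current protocol schedule, which protocol 6.1 describes as a reduced one introduced for patients already on treatment. It does not remove answers collected before. On the SAP's own Appendix 1, Cycles 5–8 were planned assessments. Neither document says how many patients reached those cycles before the reduction, or how many completed the questionnaire.

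Two further objections have some force. The examples in VI.C can be read as presupposing at least one observed cycle, so a patient never asked to complete the questionnaire is not clearly covered. That shows ambiguity; the general sentence on cycles alive without data still includes such a patient, and nothing excludes one. Protocol 9.2.8 also leaves further analyses and missing-data methods to the SAP, so a longer window is not plainly barred. That may permit Cycle 8, but it does not justify filling visits at which no questionnaire was due.

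Finally, cutting the window to Cycle 4 would drop genuine later responses from the summaries. That is a fair point against treating truncation as the only remedy.

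**Conclusion.** The point holds as a failure to align the SAP with the current protocol, combined with an imputation rule that is too broad as written. Cycle 5–8 summaries would mix observed and model-generated scores in an unknown proportion, not visible in the tables. Post-Version 7 enrollees would contribute only imputed scores to the FAS summaries; this rests on applying VI.C literally, and on the 0 of 8 count, which comes directly from the protocol. The illustrated range of about 0% to 56% depends on assumed durations and survival and is not an estimate for this trial.

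Quality of life is an exploratory objective, summarised descriptively with no test. No primary or secondary conclusion changes.

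**What to change.** In SAP VI.C, impute only assessments that were scheduled under the protocol version in force for that patient at that time. Exclude patients with no observed EQ-5D-5L in that cohort enrolment from imputation and from the quality-of-life summaries.

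In SAP XI.C, reconcile the window with protocol 9.2.8 in one of two ways: end it at Cycle 4, or keep Cycles 5–8 as observed data only. In either case show the numbers of observed and imputed scores by cycle in the tables. The second option keeps the later responses collected on the version 5 schedule.

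The cost is SAP wording, a programming filter and two count rows; no new data are needed. The downside is fewer patients in the later-cycle summaries and, with the first option, the loss of real Cycle 5–8 responses from the tables.

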2) Time variable CBD will be transformed to log form (LCBD) as below: LCBD=log(absolute value of CBD + 1)

- 3) A mixed model will be used to predict QOLtdi. The dependent variable is QOLtd; the mixed model will contain random intercept and slope subject effect, and fixed time effect (LCBD). QOLtdi will be predicted at imputed cycles.
- Compute QOLtdi re-transformed to the original scale (QOLback): This should be done by inverting the logistic regression equation.

QOLback = (logit(QOLt) - a)/b = [ln ((QOLt)/(1-QOLt)) - a]/b.

• Round imputed values up to the nearest whole number.

Note that no numerical values will be given after death, but "999" flags will be included to indicate cycles when patient was dead.

D. Multiple Study Centers

No stratification by the study centers will be utilized for analyses of efficacy or safety data.

E. Covariate Adjustment in Primary Analysis

Not planned for the primary analysis.

F. Sample Size Reassessment

No sample size reassessment is planned.

G. Interim Analyses

Interim analyses will be performed for the Phase 2 Cohort 1 and in other applicable Phase 2 cohorts that use two-stage designs, at defined timepoints, as outlined in section IV.C.

- Phase 2 Cohort 1: two interim analyses with 33% and 67% of patients' information respectively
- Phase 2 Cohort 2: with first 11 patients evaluable for response
- Phase 2 Cohort 6: with first 14 patients evaluable for response
- Phase 2 Cohort 7: with first 17 patients evaluable for response

• Phase 2 Cohort 8: with first 7 patients evaluable for response

As a result of these analyses, enrollment in a given cohort may be stopped early for futility, or in Cohort 1 for efficacy as well. Interim analyses that meet stopping criteria for futility are binding.

H. Multiple Comparisons

Alpha is controlled for the primary analysis within each Phase 2 cohorts. Corrections for multiple comparisons are not applied for the secondary or exploratory endpoints, as they are descriptive analyses.

I. Analysis Sets

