Subgroup Name	Levels	Additional Details, if applicable		
		(140 - age) * baseline weight (kg) * (0.85 if		
		female) /		
		(72 * baseline serum creatinine [mg/dL])		

K. Data Display Characteristics

Data displays produced for this study will include three types—summary tables, data listings, and figures. Unless stated otherwise, data listings will be produced for all recorded data as well as derived variables. Summary tables will be produced as specified in following sections. Figures will be produced when specified in sections to follow.

Listings will be ordered by phase, treatment (dose and schedule), cohort, patient number, and nominal visit. When expedient, additional levels of ordering hierarchy may reflect subsets of assessments within patient. Data listings will not display patient initials.

Tables will be organized differently based on the purpose of the data analysis being performed: interim safety analyses or formal interim analysis or final analysis. Data snapshots taken for the purpose of safety analysis (regulatory reporting, IB update, etc.) will be organized as outlined in Appendix 3. Table generation for interim futility and efficacy analyses as well as final analyses will be organized as specified in Appendix 3.

The summary statistics displayed will be a function of the type of data associated with the summarized assessment. Unless stated otherwise in relevant sections to follow, continuous data will be summarized with the number of non-missing values, mean, standard deviation, minimum, median, and maximum. Categorical data will be summarized with the number of non-missing values and the numbers of values equal to each of the possible values. Percentages of patients with each of the possible values will be calculated from the number of patients in the corresponding analysis set, unless stated otherwise. Some continuous variables may also be grouped into categorical levels and evaluated in frequency tables.

L. Blinded Review of Data

Not applicable for this study, as it is open label.

VII. Baseline Patient Characteristics and Disposition

A. Disposition

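### The EQ-5D change measure counts patients with problems, so it mixes deaths and imputation with quality of life and cannot be interpreted

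*SAP*

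**What the plan says.** SAP XI.C (five domains of EQ-5D-5L) asks for the number and percentage at each score, the number scoring above 1, and this change measure: "the change from baseline in the number reporting some problems in each dimension will be reported (raw and percent change"). Protocol 9.2.8 has the same rule: "Also the change from baseline in the number reporting some problems in each dimension will be reported (raw and percent change"). No within-patient domain change is specified in either document.

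Four other rules decide what that count contains.

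- **Deaths.** SAP VI.C (Missing Quality of Life Data) says "no numerical values will be given after death". Those cycles carry only a 999 flag.
- **Living patients without data.** In the same section, "QOL for cycles when patients were alive but had no QOL data will be imputed", up to death or the end of follow-up. The imputed value is then rounded upward to an integer.
- **Percentages.** SAP VI.K: "Percentages of patients with each of the possible values will be calculated from the number of patients in the corresponding analysis set, unless stated otherwise". The domain and VAS tables in XI.C state no other denominator.
- **Stacked bars.** In XI.C each bar must total 100%, which implies a denominator of patients with a score at that visit. This chart is only for the Cohort 1 EE set, and SAP VI.I says EE-based analyses are not produced for the final study report.

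The SAP summarises EQ-5D through Cycle 8. The protocol stops at Cycle 4.

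**The concern.** A change in a count over time reflects quality of life only if the same people are counted throughout. Here patients leave the count when they die or when follow-up ends, and living patients with missed questionnaires enter it with an imputed score. A fall can therefore mean deaths, and a rise can mean missed questionnaires, with no change in how patients feel.

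The percentages have a related problem. Dead patients stay in the denominator but cannot be in any score category, so the percentage at every level shrinks as deaths accumulate. A reader comparing Cycle 8 with screening could take a lower percentage with VAS below 80 as benefit. XI.C also repeats the domain summary by best response. With complete data, if non-responders die sooner (an assumption), they would show the larger fall in patients with problems.

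**Working it through.** The documents give no EQ-5D result, so there is no plan figure to reproduce. From the documents: N = 173 evaluable in Cohort 1, and the rules above. Assumed: a baseline share p = 60% with a score above 1, complete baseline data, a share d dead, and a share m of living patients without a questionnaire.

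**Step 1. Complete data in living patients.** If the share with problems among survivors is p1, the count is N × p1 × (1 - d) and its percent change is p1(1 - d)/p - 1. With p1 = p this equals -d, for any N and any p. The baseline count is 173 × 0.60 = 104.

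| Dead | Count | Change in count | Share of whole set | Share of those alive |
|---|---|---|---|---|
| 10% | 93 | -10% | 54% | 60% |
| 20% | 83 | -20% | 48% | 60% |
| 30% | 73 | -30% | 42% | 60% |
| 40% | 62 | -40% | 36% | 60% |
| 50% | 52 | -50% | 30% | 60% |

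Real worsening can be hidden. If the share among survivors rises to 70%, the count still falls once deaths exceed 1 - 0.60/0.70 = 14.3%. At 30% dead it is 173 × 0.70 × 0.70 = 85, or -18.3%.

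**Step 2. Missing data in living patients.** The imputation converts a score to a predicted probability, expit(a + b × score), with b negative if worse scores predict worse scores. An observed score of 1 gives the highest probability any observed score can have. A predicted value converts back to 1 or below only if it reaches that ceiling. The mixed model averages over worse scores and includes zeros after death, so predictions usually fall short. Anything above 1, even slightly, rounds up to at least 2 and counts as a problem.

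If a share q of imputed scores exceeds 1, the count is N(1 - d)[(1 - m)p + mq]. Take N = 100, 60 with problems at baseline, no true change, and the limiting case q = 1:

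- 80 alive, none missing: 80 × 0.60 = 48, or -20%.
- 80 alive, half missing: 40 × 0.60 + 40 = 64, or +7%.
- 70 alive, none missing: 70 × 0.60 = 42, or -30%.
- 70 alive, half missing: 35 × 0.60 + 35 = 56, or -7%.

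At 20% dead the sign turns at m = pd/[(1 - p)(1 - d)] = 0.12/0.32 = 37.5% missing. The result is sensitive to q: with 80 alive, half missing and q = 0.90, the count is 24 + 36 = 60, no change at all.

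Simulating the SAP's imputation steps under assumed inputs gave 98-99% of imputed domain scores above 1. With 14-18% dead at Cycle 4, the count changed by -12% with no missing data and by +13% with half missing. The share depends on the inputs, so these figures only illustrate the mechanism.

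**Step 3. Percentages.** Under the VI.K default with 30% dead and complete data in the living, the table shows 0.40 × 0.70 = 28% without problems and 42% with. These total 70%. The stacked bar for the same visit must total 100%, so the table and the chart cannot share a denominator.

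**Step 4. Does an alive-only denominator cure it?** If deaths are unrelated to problems, the share stays at 60% (last column of the table). If patients with problems die twice as often, the death rate among the others is x = d/(2p + 1 - p) = d/1.6, and the share among survivors is p(1 - 2x)/(1 - d). At 30% dead, x = 0.1875 and the share is 0.375/0.70 = 53.6%. At 20% and 40% dead it is 56.2% and 50.0%. Survivor selection remains, so a paired change and a row for deaths are also needed.

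**The case against.** A reader might infer that the table must show improvement simply because patients die, that the percent change equals survival minus one, and that the bias always favours the drug. The documents do not support this. The formula holds only with complete data in living patients and a constant problem rate. The SAP imputes living patients and rounds up, and Step 2 shows the count can rise despite deaths.

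Other points also stand:

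- XI.C gives a number, not a percentage, for patients with some problems. That percentage has to be obtained by adding score levels 2 to 5. Among percentages of this kind, only the one for VAS below 80 is explicit.
- VI.K requires the number of non-missing values, and the percentage without problems falls as well, so a careful reader could notice attrition. But imputation may fill that number for living patients, and the SAP does not say that the death flags are tabulated.
- No death rate, missing-data rate or baseline problem rate is given. A large effect in every cohort is not established, and Cohort 2 enters in remission and may be little affected.
- Quality of life is exploratory, there is no comparator arm, and no test depends on it.

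These points limit the direction, size and consequence. They do not make the change in a count interpretable.

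**Conclusion.** The point holds as a defect in an exploratory, descriptive output. As specified, the domain change combines true change, deaths, end of follow-up and imputation in one number, and the documents give no means of separating them. Under assumed inputs with no true change, the reported value ranges from -50% (half dead, complete data) to +7% (20% dead, half the living missing, every imputed score above 1). These are illustrations, not estimates. The percentages at each score and for VAS below 80 have a separate, simpler fault: their default denominator includes patients who can no longer have a score, and it disagrees with the stacked bars. That chart is dropped from the final report, so the remaining tables need a clear denominator. The SAP's longer window, to Cycle 8, leaves more time for deaths. Correction is worthwhile because it is cheap, but no efficacy conclusion depends on it.

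**What to change.** In SAP XI.C and protocol 9.2.8, replace the change in number with two measures:

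- the percentage with a score above 1 among patients alive with a score at that cycle;
- the within-patient change (better, same, worse) among patients with both a baseline score and a score at that cycle.

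Show both for observed scores alone and with imputation. At each cycle, give the numbers dead, missing and imputed. State the visit-specific denominator as an exception to SAP VI.K for the domain tables and the VAS below 80 table.

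The cost is wording and table shells, with a few more rows and no new data collection. Both measures still describe survivors only, and a table footnote should say so.
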